6 STUDY EVALUATIONS AND MEASUREMENTS

6.1 Screening Measures

6.1.1 Medical Record Review

Medical record review will assess initial eligibility criteria for women in the postpartum period.

- Age (years)
- Gestational age at recent delivery
- Insurance
- History of sterilization procedure
- Timing of first prenatal visit
- Number of prenatal visits
- Tobacco use prior to or during pregnancy
- Gestational Diabetes
- Pregnancy Induced Hypertension
- Treatment for depression or anxiety during pregnancy
- Weight and height
- Planned site of infant pediatric care
- Plans to move out of the area during the upcoming six months

The last two items listed above (planned site of infant pediatric care and plans to move out of the area during the upcoming six months) may not be consistently documented in the health record. Potential participants will be informed that we are seeking these characteristics in study participants.

6.2 Measures of Treatment Feasibility and Acceptability (Primary Outcome)

The primary outcome of this study is to assess feasibility and acceptability of the Care Coordination After Preterm Birth intervention. We will assess feasibility and acceptability using the following measures.

- *Screening rate (feasibility)*: The study team will compare the number of potentially eligible participants to those who complete screening questionnaires. The number of potentially eligible participants will be considered the number of preterm births with Medicaid insurance in a given month.
- *Recruitment rate (feasibility)*: The study team will track the proportion of eligible women screened who enroll in the study.
- *Reasons for non-participation (acceptability)*: For women who decline screening or enrollment we will ask them, if they are willing, to provide reasons for non-participation and potential study modifications that might have encouraged them to participate. Responses will be tabulated and reviewed for potential themes.
- *Retention rate (feasibility)*: The study team will track the proportion of enrolled participants who complete the intervention and the study assessments.
- *Assessment process (feasibility)*: The study team will track the proportion of the baseline, 3-month, and 6-month assessments that are completed.

- *Intervention usability (feasibility)*: Study interventionists will keep records of barriers and facilitators of the intervention content and procedures.
- *Family engagement and adherence (feasibility)*: Study interventionists will keep track of the proportion of contacts initiated that are completed, contacts initiated by participants, and participant use of resources and strategies discussed during the intervention, based on participant feedback.
- *Intervention fidelity (feasibility)*
 - *Care coordination fidelity*: We will quantify interventionist completion of screening tools, as well as other tasks outlined in the care plan, including focused education, navigation, and addressing barriers to care, screening.
 - *Motivational interviewing fidelity*: OnePass is a validated tool used to evaluate MI practice and assess fidelity based on review of a single session, using 23 items to assess MI components.⁶¹ This tool yields a global score while also identifying specific areas for additional practice and training. Scores range from 1 – 7 with 5 considered a minimum for competence. Interventionists will complete at least one OnePass within a month of starting MI sessions with participants.
- *Intervention acceptability (participants)*: Care givers will complete a brief (10 – 15 minutes) audio-recorded, open-ended qualitative interview with questions related to acceptability domains such as attitude towards intervention, intervention burdens, perceived effectiveness of the intervention, willingness to participate again or recommend intervention to a friend, and satisfaction with the intervention.
- *Intervention acceptability (participants)*: We will use an adapted version of the validated Acceptability of the Intervention Measure to measure acceptability quantitatively.

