4.4 Study Population

4.4.1 Inclusion Criteria

- 1) Females age 14 – 45.
- 2) History of preterm birth at < 34 weeks gestation OR history of preterm birth at 34 – 36 weeks gestation with risk factors for recurrent preterm birth including: low preventive care utilization, tobacco use, obesity, depression or anxiety, history of unmet contraceptive needs.
- 3) Intention to seek infant pediatric primary care at one of the two study sites (Karabots and Cobbs Creek).
- 4) Medicaid insurance.

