5 STUDY PROCEDURES

5.1 Screening phase

Procedures for screening are described above in greater detail (section 3.1.1). The screening phase will include the following activities. Details of data collection tools and definitions are included below in section 5.

- Health record review by study team member to assess gestational age.
- Phone, in person, or video confirmation of eligibility and scheduling of informed consent and baseline assessment.

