7.4 Statistical Methods

7.4.1 Primary outcome: Feasibility data

We will examine the following quantitative feasibility and acceptability outcomes through the use of descriptive statistics, which include means for continuous variables and proportions for categorical variables. In some cases, we will compare them to a priori goals for feasibility. See above (Section 5) for more detail about measurement of these outcomes.

- Screening rate: Proportion of potentially eligible participants screened.
- Recruitment rate: Proportion of screened women who enroll.
- Retention rate: Proportion of enrolled participants who complete the intervention and the study assessments.
- Assessment process: Proportion of the baseline, 3-month, and 6-month assessments that are completed.
- Family engagement and adherence: Proportion of contacts initiated that are completed within 3 days will be compared to an a priori threshold of 80%, # of contacts initiated by participants, # of recommended resources utilized.
- Intervention fidelity
 - Care coordination fidelity: # of screenings completed, # of care plan goals achieved
 - Motivational interviewing fidelity: OnePass score will be compared to an a priori threshold of 5, considered a minimum threshold for competence.

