9.5 Recruitment Strategy

Potentially eligible participants will be identified by screening health records in the newborn nursery and the neonatal intensive care unit at the Hospital of the University of Pennsylvania or by identifying women whose infants present for primary care at Karabots or Cobbs Creek. Chart review of women within four weeks of delivering a preterm infant (< 37 weeks) will assess for potential modifiable health risks, as well as other inclusion and exclusion factors. Next, potentially eligible women will be approached for recruitment and informed consent. Two eligibility factors may not be consistently documented in a health record (planned site of pediatric care for infant, any plans to move out of the area in the upcoming six months). These factors will be confirmed verbally before proceeding with other enrollment activities. Women will be approached by study staff via phone or in person during hospitalization following delivery, or when visiting their infant in the hospital. In the event that conditions related to COVID or other unanticipated events prevent the physical presence of study staff in the clinical setting we will develop a flier to be distributed at

discharge, allowing women to call a number to opt out of the study. This flier will be submitted to the IRB for review prior to use. We are requesting a waiver of consent and authorization for screening. Preliminary chart review estimates that approximately 100 eligible women deliver at HUP each year and choose to take their infants for pediatric care at one of the study primary care sites. We therefore expect it will be feasible to enroll 106 participants over two years.

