9.6 Informed Consent/Accent and HIPAA Authorization

9.6.1 Waiver of HIPAA Authorization to Screen Medical Records

We are requesting a waiver of HIPAA authorization to screen health records for women following birth to identify potentially eligible participants. This will ensure that women who are contacted appear to be eligible based on chart review.

The use of health record data for eligibility screening involves no more than a minimal risk to the privacy of individuals. Identifiers for potentially eligible participants (name, room number, telephone number) will be stored in a secure REDCap database and will be destroyed within two weeks for any potentially eligible participant who has not been contacted or who has been contacted by declined enrollment. As noted above, screening summary data will be retained (number potentially eligible, number completed screening, number consented to study participation) but these data will not include any protected health information. Individual screening data will not be used for study purposes (beyond screening). Screening data will not be reused or disclosed for any reason.

The research could not practicably be conducted without the waivers. Due to the large number of women delivering at HUP and the frequency of rapid discharges, a requirement to obtain HIPAA authorization for screening could introduce bias into recruitment with women with longer length of stay more likely to be identified as potentially eligible. In addition, the research could not be conducted without access to this data as there would be no practicable way to identify potentially eligible women.

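### The screening rate divides by all Medicaid preterm births, so women ruled out on chart review count as unscreened and the rate understates reach among potentially eligible women

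*Combined protocol and SAP*

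**What the plan says.** Section 6.2 describes the screening rate as a comparison: "The study team will compare the number of potentially eligible participants to those who complete screening questionnaires". It then defines the denominator: "The number of potentially eligible participants will be considered the number of preterm births with Medicaid insurance in a given month". No hospital is named. Section 7.4.1 reports the measure descriptively, with no target: "Screening rate: Proportion of potentially eligible participants screened".

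The recruitment text uses the term differently. In section 9.5, charts of women within four weeks of a preterm delivery are reviewed for modifiable risks and the other entry criteria, and the potentially eligible women are approached after that. Section 9.6.1 gives the purpose of the record screen: "This will ensure that women who are contacted appear to be eligible based on chart review".

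Section 9.5 finds women through newborn-unit records at the Hospital of the University of Pennsylvania (HUP) "or by identifying women whose infants present for primary care at Karabots or Cobbs Creek". The abstract and section 4.1.1 mention only the HUP units as the source.

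Screening itself, in section 5.1, is a record review followed by "Phone, in person, or video confirmation of eligibility and scheduling of informed consent and baseline assessment". Section 6.1.1 lists the items taken from the record.

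**The concern.** One term has two meanings, and the wider meaning is the denominator of a primary feasibility measure. A woman excluded on her chart is handled correctly if nobody contacts her, but under section 6.2 she counts as not screened. A low rate could mean that staff failed to reach the target women, or that many Medicaid preterm births did not meet the other criteria. The reader could not tell which.

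The numerator is also unclear. It counts completed questionnaires, but Table 1, section 5.1 and section 6.1 describe only record review and a spoken confirmation before enrollment. The screening tools that the care coordinator uses (sections 4.1.2 and 6.2) come after enrollment.

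Timing matters. Section 9.6.1 keeps summary counts only, destroys identifiers within two weeks for women not contacted or who decline, and bars other use of individual screening data. If the number potentially eligible is tallied under the wrong meaning, the study records may not allow the right rate to be rebuilt.

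**Working it through.** **1. The plan's own figures.** The screening rate has no stated value or target. The only figure on the pool is in section 9.5: "Preliminary chart review estimates that approximately 100 eligible women deliver at HUP each year", counting those who choose a study site. Over two years that is 100 × 2 = 200 women, and the maximum of 106 participants is 106 / 200 = 53% of them. This is consistent, but it concerns enrollment and does not give a screening rate.

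**2. Which entry criteria the section 6.2 count applies.**

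| Criterion (4.4.1, 4.4.2) | Applied in the 6.2 count? | On the 6.1.1 record list? |
|---|---|---|
| "Females age 14 – 45" | No | Yes |
| Preterm birth, with a risk factor if at 34–36 weeks | Preterm yes, risk factor no | Gestational age and several risk factors; unmet contraceptive need is not listed |
| Planned pediatric site | No | Yes, may be undocumented |
| Medicaid | Yes | Yes |
| Sterilization | No | Yes |
| Moving or transferring pediatric care | No | Moving plans, may be undocumented |
| Limited English proficiency | No | No |

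Of seven criteria, one is applied in full, one in part and five not at all. Several of those left out can be settled on the chart before any contact.

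**3. Effect on the rate.** Within one catchment, let D be Medicaid preterm births, C the women not excluded on chart review, and S the women who complete screening. Then

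rate under 6.2 = S / D = (S / C) × (C / D).

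S / C is reach among potentially eligible women. C / D is the share surviving chart review, and it is also the ceiling on the 6.2 rate. The documents give neither C nor D.

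If the count means HUP births, and chart review does not wrongly drop eligible women, C is at least about 100. So 100 / D is the lowest value that the ceiling could take. For assumed D of 150, 200, 300 and 400 a year it is 67%, 50%, 33% and 25%. The upper limit is 100%, when C = D.

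Illustration, with both numbers assumed: D = 300 and C = 220. The ceiling is 220 / 300 = 73%. If 80% of chart-eligible women are screened, S = 0.80 × 220 = 176. Section 6.2 then reads 176 / 300 = 59%, against 176 / 220 = 80%. At D = 300, a true reach of 80% could read anywhere from 0.80 × 100 / 300 = 27% (C = 100) to 80% (C = 300).

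**4. Catchment.** If the count means HUP births, a woman identified at a primary care site who delivered elsewhere enters the numerator only. Assume D = 200 and 80 screened women who delivered at HUP: 80 / 200 = 40%. If 10%, 20% or 30% of all screened women delivered elsewhere, the numerator becomes 80 / 0.9 = 89, 80 / 0.8 = 100 or 80 / 0.7 = 114, and the rate 44%, 50% or 57%. This acts against the effect in step 3, so the net direction would be uncertain.

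**5. Unit.** The denominator counts births and the numerator counts women. Multiples may count more than once; the text does not say.

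**The case against.** The strongest defense is that section 6.2 states its denominator openly and chooses a count available before individual review. No such denominator can apply every criterion: sections 6.1.1 and 9.5 accept that pediatric site and moving plans may be missing from the chart, and English proficiency is not on the record list. The ratio still describes reach into all Medicaid preterm births. It is one of many measures and has no threshold; the stated thresholds in section 7.4.1 concern completed contacts (80%) and the OnePass score (5). The abstract and section 4.3.2 end enrollment once feasibility is established, but do not link that to this rate. The questionnaire wording may be only a label for a form used at the spoken check, and multiple counting of twins is a possibility, not a stated rule.

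Most of this stands and limits the consequence. It does not remove the conflict. Criteria that the chart can settle are applied before contact, and the women they exclude are then counted against screening. The counts retained under section 9.6.1 do not resolve this, because the number potentially eligible is the ambiguous quantity.

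Three stronger readings are tempting and not supported:

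- *The primary care route lies outside the denominator.* Section 6.2 names no hospital, and women found at the clinics may have delivered at HUP. The documents show only that the catchment is unspecified.
- *The rate can be at most 100 / D.* Women found ineligible at the spoken confirmation have still been screened and count in the numerator. The roughly 100 women have already chosen a study site, so they are not the whole chart-eligible group.
- *The rate does not measure screening reach at all.* It measures reach into a wider population than its label says.

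**Conclusion.** The concern holds as a definitional fault in a primary feasibility measure. Within a common catchment, the section 6.2 denominator understates reach among potentially eligible women by the factor C / D and confuses ineligibility with failed outreach. The size of that factor cannot be computed from the documents; the figures in steps 3 and 4 rest on assumed counts and show only how far the reading could move. The catchment and the numerator event also need definition. Because the measure is descriptive and has no threshold, what is at stake is the interpretation of the rate and its use in planning later work. It should be corrected while the counts can still be tallied properly.

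**What to change.** In sections 6.2 and 7.4.1, define the screening rate as unique women who complete the eligibility confirmation in section 5.1, divided by unique women not excluded on chart review. Keep women with an undocumented pediatric site or undocumented moving plans in the denominator, since only the confirmation can settle those items. Replace the reference to questionnaires with that confirmation.

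Name the hospital or hospitals whose births are counted, and report the HUP and primary care site routes separately. Keep all Medicaid preterm births as the top line of a flow diagram, followed by women not excluded on chart review, approached, screened, eligible and enrolled. Use one meaning of *potentially eligible* in sections 6.2, 9.5 and 9.6.1.

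The cost is small: wording changes, a running tally of chart-review exclusions, and one field for recruitment route. Section 9.6.1 already plans to keep the numbers potentially eligible, completing screening and consenting.

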6.3 Measures of Modifiable Health Behaviors and Sociodemographic characteristics

6.3.1 Modifiable health behaviors

Modifiable health behaviors will be measured at baseline, 3-months, and 6-months as described here. We will also measure autonomous motivation and autonomy support as outcomes related to the motivational interviewing component of the project. Details are provided here.

- **Care utilization** will be abstracted from the medical record whenever possible. Available data will include all data from the CHOP and Penn health records. In addition, participants will be asked to report on all health care.
- **Tobacco use** will be assessed as any tobacco use in the past 30 days, a meaningful measure of continuous abstinence.⁶²
- **Contraceptive use** will be assessed by asking about any current contraceptive methods.
- **Mental health symptoms** will be measured with the Edinburgh Postnatal Depression Scale – This 10 item rating scale has been validated in diverse populations (range 0 – 30, Cronbach alpha 0.87). and widely used in both clinical

practice and research settings. In clinical settings, a cutoff of 10 is typically considered concerning for potentially meaningful clinical symptoms of depression.⁶³

- **Perceived stress** will be measured using the Perceived Stress scaled. This 10-item scale has been validated in diverse populations (range 0 – 40, Cronbach alpha 0.80).
- **Participant weight** will be measured at baseline and 6 months. All efforts will be made to obtain a weight in a clinical setting (either during a pediatric visit or from the participants own health record). If these efforts are not successful, we will record participant reported weight.
- **Autonomy support** reflects individuals' perception of the degree to which the health care team understands individuals' perspectives and trusts they will make the best decisions for themselves. Autonomy support will be measured with the short form of the Health Care Climate Questionnaire (6 items, range 6 – 42, Cronbach alpha 0.82).⁶⁴
- **Autonomous motivation** reflects the degree to which individuals are driven by concerns consistent with their own values or identity. Validated tools exist to measure autonomy support and autonomous motivation.^{64,65} Autonomous motivation will be measured using the Autonomous Motivation and External Regulation scales of the Treatment Self-Regulation Questionnaire (10 items, range 7 – 70, Cronbach alpha 0.90).⁶⁵
- **Sleep-related impairment** will be measured using the PROMIS Item Bank 8-item measure (range 8 – 40, Cronbach alpha 0.89).

6.3.2 Sociodemographic factors

The following sociodemographic factors will be assessed at baseline only:

- Maternal age (years) (Health record review)
- Race (participant self-report)
- Ethnicity (Participant self-report)
- Educational attainment (Participant self-report)
- Estimated household income (Participant self-report)
- Prior pregnancies (Health record review)
- Complications of pregnancy including gestational diabetes or pregnancy-induced hypertension (Health record review)
- Chronic conditions including diabetes, asthma, hypertension, depression, or anxiety (Health record review)

The following demographic factors will be assessed at baseline and at 6-month follow-up and will both be collected via participant self-report:

- Household composition
- Relationship with other biological parent of child (if applicable) including married, cohabitating, not cohabitating but still in a relationship, no longer in a relationship but other parent actively involved in parenting

The following potential barriers to positive health behaviors will be assessed at baseline and at 3-month and 6-month follow-up and will all be collected via participant self-report:

- Health insurance will be assessed using item structure used in the Behavioral Risk Factors Surveillance Survey (at time of enrollment all participants should have Medicaid, however this may vary over time).⁶⁶
- Transportation needs will be assessed using items from the WellRx screening, which was developed in a Family Medicine setting and has been widely used.⁶⁷
- Child care will be assessed using items from the WellRx screening, which was developed in a Family Medicine setting and has been widely used.⁶⁷
- Food insecurity will be assessed with a two item screen that has been previously validated with families in pediatric settings. The two items are “within the past 12 months we worried whether our food would run out before we got money to buy more” and “within the past 12 month the food we bought just didn’t last and we didn’t have money to get more.”⁶⁸
- Employment status will be assessed using item structure used in the Behavioral Risk Factors Surveillance Survey and the Pregnancy Risk Assessment Monitoring System.^{66,69}

6.4 Safety Evaluation

Participant safety will be monitored by adverse events throughout the study. Please see the Data Safety and Monitoring Plan (Section 8.4.1) for further information.

7 STATISTICAL CONSIDERATIONS

7.1 Primary Endpoint

The primary endpoints are overall rating of intervention feasibility and acceptability of the intervention.

